18.0 INFORMED CONSENT PROCEDURES

Before protocol-specified procedures are carried out, consenting professionals will explain full details of the protocol and study procedures as well as the risks involved to patients prior to their inclusion in the trial. Patients will also be informed that they are free to withdraw from the study at any time. All patients must sign an IRB-approved consent form indicating their consent to participate. This consent form will meet the requirements of the code of federal regulations, and the IRB of this center. The consent form will included the following:

1. The nature and objectives, potential toxicities and benefits of the intended study.
2. The length of therapy and the likely follow-up required.

3. Alternatives to the proposed therapy. This will included available standard and investigational therapies. In addition, patients will be offered an option of supportive care.
4. The name of the investigator (s) responsible for the protocol.
5. The right of the patient to accept or refuse treatment and to withdraw from participation in the study.

Each patient and consenting professional will sign the consent form in triplicate. One original signed consent form will become part of the patient's medical record, another original signed consent form will be stored in the patient's research file, and the third original signed consent form will be given to the patient.

19.0 SATELLITE SITE PATIENT ENROLLMENT PROCESS

Once screening procedures are completed. The following documentation must be provided to GI Clinical Research Manager (CRM) for review and enrollment:

- Signed signature page of informed consent;
- Signed and dated by Sub-Investigator and coordinator:
 - I/E criteria checklist;
 - Child-Pugh score form;
 - RECIST tumor assessment worksheet;
 - Subject Eligibility Verification form;

Once required materials are received and verified by the CRM. The enrollment verification form (EVF) will be signed and a study ID assigned to the patient. Once the signed EVF has been received by study staff the patient is ready to begin therapy.

21.0 Appendices

Appendix A ECOG Performance Status

Grade	ECOG
0	Fully active, able to carry on all pre-disease performance without restriction
1	Restricted in physically strenuous activity but ambulatory and able to carry out work of a light or sedentary nature, i.e., light house work, office work
2	Ambulatory and capable of all self-care but unable to carry out any work activities. Up and about more than 50% of waking hours.
3	Capable of only limited self-care, confined to bed or chair more than 50% of waking hours.
4	Completely disabled. Cannot carry on any self-care. Totally confined to bed or chair.
5	Dead

Appendix B Child-Pugh Score

Measure	1 point	2 points	3 points
Total bilirubin (mg/dl)	<2.0	2.0-3.0	>3.0
Serum albumin (g/l)	>3.5	2.8-3.5	<3.5
INR	<1.7	1.7-2.2	>2.2
Ascites	None	Mild (based on clinical findings)	Severe (based on clinical findings)
Hepatic Encephalopathy	None	Controlled Medically	Refractory

5-6 points Child-Pugh A
 7-9 points Child-Pugh B
 10-15 points Child-Pugh C

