	
 2. Locally advanced or metastatic disease. 
 a. Patients with locally advanced disease must have disease deemed to be unresectable or not eligible for hepatic transplantation by surgical oncologist or transplant physician 3. Measurable disease, defined as lesions that can accurately be measured in at least one dimension (longest diameter to be measured) according to Response Evaluation Criteria in Solid Tumors (RECIST, version 1.1) at least 2 cm with conventional techniques or at least 1 cm with spiral computed tomography. 4. Child-Pugh Score A or B7. 5. Age \geq 18 years. 6. ECOG Performance Score of 0-2. 7. Absolute neutrophil count \geq 1,200 cells/mm³. 8. Platelet count \geq 70,000 cells/mm³. 9. Total Bilirubin \leq 3.0 mg/dl. 10. Hemoglobin \geq 8.5 g/dl. 11. INR \leq 1.8 (therapeutic anticoagulation allowed as long as medically indicated.) 12. Creatinine \leq 1.5 times upper limit of normal. 13. Women of childbearing potential must have a negative pregnancy test. 14. No clinically significant episode of gastrointestinal bleeding within the previous 30 days. 15. Men and women of childbearing potential must be willing to consent to using effective contraception while on treatment and for at least 3 months thereafter. 16. At least 4 weeks since prior locoregional therapy including surgical resection, radiotherapy, hepatic arterial embolization or chemoembolization, radiofrequency ablation, percutaneous injection or cryoablation (treatment of target lesion only, non-target lesions can be treated with locoregional therapy). Provided the target lesion increased in size by 25% or more or the target lesion
--	---

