6.0 CRITERIA FOR SUBJECT ELIGIBILITY

6.1 Subject Inclusion Criteria

1. Patients must have a diagnosis of hepatocellular carcinoma by at least one criterion listed below:
 - a. Histologically confirmed hepatocellular carcinoma
 - b. Axial imaging consistent with liver cirrhosis and at least one solid liver lesion ≥ 2 cm with early enhancement and delayed enhancement washout regardless of alpha-fetoprotein (AFP) levels.
 - c. AFP ≥ 400 ng/ml and evidence of at least one solid liver lesion ≥ 2 cm regardless of specific imaging characteristics.
2. Locally advanced or metastatic disease.
 - a. Patients with locally advanced disease must have disease deemed to be unresectable or not eligible for hepatic transplantation surgical oncologist or transplant physician.
 - b. Measurable disease, as defined as lesions that can accurately be measured in at least one dimension (longest diameter to be

measured) according to Response Evaluation Criteria in Solid Tumors (RECIST, version 1.1) at least 2 cm with conventional techniques or at least 1 cm with spiral computed tomography.

3. Child-Pugh Score A or B7.
4. Age \geq 18 years.
5. Eastern Cooperative Oncology Group (ECOG) Performance Score of 0-2.
6. Absolute neutrophil count \geq 1,200 cells/mm³.
7. Platelet count \geq 70,000 cells/mm³.
8. Total bilirubin \leq 3.0 mg/dl.
9. Hemoglobin \geq 8.5 g/dl.
10. INR \leq 1.8 (therapeutic anticoagulation allowed as long as medically indicated.)
11. Creatinine \leq 1.5 times upper limit of normal.
12. Women of childbearing potential must have a negative pregnancy test.
13. No clinically significant episode of gastrointestinal bleeding within the previous 30 days.
14. Men and women of childbearing potential must be willing to consent to using effective contraception while on treatment and for at least 3 months thereafter.
15. At least 4 weeks since prior locoregional therapy including surgical resection, radiotherapy, hepatic arterial embolization or chemoembolization, radiofrequency ablation, percutaneous injection or cryoablation (treatment of target lesion only, non-target lesions can be treated with locoregional therapy). Provided the target lesion increased in size by 25% or more or the target lesion was not treated with locoregional therapy.
16. Greater than 4 weeks since prior interferon therapy.
17. Greater than 4 weeks since prior and no concurrent use of rifampin or St John's wort.
18. Prior antiviral therapy is allowed.
19. Life expectancy $>$ 12 weeks.

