8.0 PRETREATMENT EVALUATION

8.1 Phase I component

To be completed within 30 +/- 3 days of starting therapy;

- CT abdomen or MRI abdomen with liver protocol
- A 12 lead electrocardiogram
- Bilateral venous duplex of lower extremities
- Documentation of all measurable or non-measurable disease parameters including radiographic imaging procedures within four weeks of study entry, and measure of biochemical marker of disease (if applicable) within four weeks of study entry. The RECIST criteria as defined by CTEP (<http://ctep.info.nih.gov/policies>) define measurable and non-measurable disease.
- Signed informed consent for study participation.

To be completed within 14 +/- 3 days of starting therapy:

- History and physical examination, including height, weight, calculated body surface area (BSA), vital signs (temperature, pulse rate, respiration rate, blood pressure), and performance status (ECOG). See Appendix A for ECOG scale.
- Serum pregnancy test for all women of childbearing potential within 14 days of starting therapy. If the test result is positive, the patient will not be allowed to participate in the study.
- Laboratory evaluation and coagulation parameters
 - CBC with differential and platelet count
 - Serum chemistries (Na, Cl, BUN, Creatinine, K, bicarbonate and glucose), albumin and calcium
 - Liver function tests (AST, ALT, alkaline phosphatase, total bilirubin),
 - Coagulation parameters (aPTT, PT and INR)
 - Urinalysis, record protein, glucose and blood
- Recording of concomitant medications

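### The albumin row of the Child-Pugh table gives values from 2.8 to just under 3.5 two different scores, and its unit (g/l) does not fit its cut-points, although the score decides eligibility.

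*Combined protocol and SAP*

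**What the plan says.** The protocol summary (section 1.0) and section 6.1 both admit patients with "Child-Pugh Score A or B7". Neither defines the score. The only scoring bands are in Appendix B, whose columns run "Measure 1 point 2 points 3 points" and whose albumin row is "Serum albumin (g/l) >3.5 2.8-3.5 <3.5". Class A is 5-6 points and the next band is "7-9 points Child-Pugh B", so B7 means exactly 7 points and the entry rule is a total of 7 or fewer.

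Section 6.1 also limits total bilirubin to 3.0 mg/dl and INR to 1.8, with a remark in brackets allowing therapeutic anticoagulation. It sets no separate albumin limit. Sections 8.1 and 8.2 list albumin among the screening chemistries without a unit or cut-off. Section 19.0 requires satellite sites to send in a signed "Child-Pugh score form", which is not reproduced.

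**The concern.** The row has two faults, which arise under different readings of it.

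- **Overlap.** The 3-point cell takes everything below 3.5, while the 2-point cell runs from 2.8 to 3.5. A value between those bounds sits in both. The bilirubin and INR rows of the same table have no such overlap.
- **Unit.** The cut-points are labelled g/l. For albumin in the tens of g/l, every patient exceeds 3.5 and scores 1 point.

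The stake is eligibility. One point separates 7 from 8, so under the first fault two sites could score the same patient and reach opposite answers. Under the second, low albumin adds nothing to the score, so patients could enter whom the same cut-points read in g/dl would exclude. Someone verifying eligibility against the protocol could not obtain a single answer. The recorded class can also move between A and B7. That affects the description of the population, because section 3.1 says the trial that gave the 5.5-month sorafenib benchmark enrolled Child-Pugh A patients.

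**Working it through.** There is no stated figure to reproduce; the check scores the table literally and counts the consequences.

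**1. Literal scoring of the albumin row** (numbers as printed, unit ignored)

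| Albumin | Cells that apply |
|---|---|
| 2.79 | 3 points |
| 2.8, 3.0, 3.49 | 2 and 3 points |
| 3.5 | 2 points |
| 3.51 | 1 point |

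The overlap is 2.8 ≤ albumin < 3.5.

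**2. Possible scores on the other four items.** The section 6.1 limits cap two items: bilirubin up to 3.0 mg/dl scores 1 or 2, and INR up to 1.8 scores 1 or 2. Ascites and encephalopathy can each score 1, 2 or 3. This gives 2 × 2 × 3 × 3 = 36 patterns, with these sums:

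| Sum of other four items | 4 | 5 | 6 | 7 | 8 | 9 | 10 |
|---|---|---|---|---|---|---|---|
| Patterns | 1 | 4 | 8 | 10 | 8 | 4 | 1 |

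**3. Eligible patterns.** A patient is eligible if the sum plus the albumin score is 7 or less.

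- Albumin scores 1: sum ≤ 6, so 1 + 4 + 8 = 13 patterns.
- Albumin scores 2: sum ≤ 5, so 1 + 4 = 5 patterns.
- Albumin scores 3: sum ≤ 4, so 1 pattern.

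**4. Effect of the overlap.** 5 − 1 = 4 patterns change eligibility. In each, exactly one other item scores 2 and the rest score 1, so the sum is 5 and the total is 5 + 2 = 7 (eligible) or 5 + 3 = 8 (not eligible). One of the four has INR as the raised item, which under the entry limit means an INR of 1.7 to 1.8. If all four other items score 1, the total is 4 + 2 = 6 (class A) or 4 + 3 = 7 (B7). The patient is eligible either way, but the class differs.

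**5. Effect of the unit.** The documents give no albumin range. Assume about 20-50 g/l; any range wholly above 3.5 g/l gives the same result. Read literally, albumin then always scores 1 and 13 of 36 patterns are eligible. Take a patient at 25 g/l, which is 25 / 10 = 2.5 g/dl. Literal reading: 25 > 3.5, so 1 point. The same cut-points in g/dl: 2.5 < 2.8, so only the 3-point cell applies. With 6 points on the other items, the total is 6 + 1 = 7 (enters) or 6 + 3 = 9 (does not). At this albumin value, 13 − 1 = 12 patterns differ.

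**6. Sensitivity to the INR limit.** If the anticoagulation remark is read as an exception to the INR limit, INR can score 3 and there are 2 × 3 × 3 × 3 = 54 patterns. The literal-g/l count becomes 14 of 54, and 14 − 1 = 13 patterns differ. The 4 overlap patterns do not change.

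**The case against.** The strongest reply is that this is a typographical slip that an experienced scorer would see through. If the 3-point cell overrode the 2-point cell, the latter would apply only at exactly 3.5 and its lower bound of 2.8 would have no purpose, so only one reading keeps all three columns working. The unit slip is easy to spot as well: bilirubin and hemoglobin are given per decilitre elsewhere in the protocol, and the literal reading needs a scorer not to notice that every patient scores 1. The entry criterion does not cite Appendix B by name, satellite sites use a form that may be correct, and no analysis in section 15 uses Child-Pugh class. Pattern counts also weight rare combinations equally with common ones.

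Much of this stands as a limit on likely harm. It is unknown whether any patient was misclassified, and the two faults do not add up: under literal g/l and the assumed range, nobody falls in the overlap. The 12-pattern figure belongs to the less plausible reading and should be treated as secondary. But none of this makes the row correct. The documents supply no other albumin bands or unit to settle it, and the row feeds an entry threshold. A reading fault in the PDF is unlikely, since every row has its full set of cells and the neighbouring rows are intact.

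**Conclusion.** The concern holds. As printed, the row scores albumin from 2.8 to just under 3.5 twice, and its unit does not fit its cut-points. The overlap depends only on the table's own text. Its effect on entry is confined to patients whose other four items total exactly 5: 4 of the 36 patterns. The unit fault rests on the assumed albumin range of about 20-50 g/l. How many patients either fault touches is unknown, because the documents give no albumin distribution and do not show the score form. Sample size and the planned analyses are not directly affected. This should be corrected because it leaves an eligibility threshold undefined.

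**What to change.** The sponsor should reconcile the albumin row so that its three cells are mutually exclusive and its unit matches its cut-points. The 2-point cell's lower bound and the neighbouring rows indicate the intended pattern, but the values are for the sponsor to settle. Next, reissue Appendix B to all sites and check that the satellite-site Child-Pugh form agrees with it. Then re-score any screened patient whose albumin score changes, using the albumin collected under sections 8.1 and 8.2, and document any change in eligibility. It would also help if the inclusion criterion cited Appendix B.

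The cost is a one-row correction, a check of one form, and re-scoring from existing data. No new procedure is needed.

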Appendix C NYHA Classification

Class	Patient Symptoms
I	No limitation of physical activity. Ordinary physical activity does not cause undue fatigue, palpitation, or dyspnea (shortness of breath).
II	Slight limitation of physical activity. Comfortable at rest, but ordinary physical activity results in fatigue, palpitation, or dyspnea.
III	Marked limitation of physical activity. Comfortable at rest, but less than ordinary activity causes fatigue, palpitation, or dyspnea.
IV	Unable to carry out any physical activity without discomfort. Symptoms of cardiac insufficiency at rest. If any physical activity is undertaken, discomfort is increased

